5. STUDY DRUG(S)/DEVICE(S)

5.1 Study Drug/Device Information

The participants will receive either Lotemax or Soothe Tired Eye Drop.

Lotemax

Lotemax (loteprednol etabonate) 0.5% is a prescription-only, preserved ophthalmic suspension supplied by Bausch & Lomb, Inc. Lotemax (loteprednol etabonate) 0.5% has been approved by the FDA for treatment of ocular inflammation with a maximum dosing frequency of 24 drops per eye per day. It is a C-20 ester-based corticosteroid, with a potent anti-inflammatory efficacy, but decreased impact on intraocular pressure (IOP) compared to other corticosteroids, which may increase IOP. The medication will be applied topically to both eyes for 6 weeks with the following regimen: four times a day for 2 weeks, twice daily for 2 weeks, and once daily for 2 weeks.

Soothe Tired Eyes Lubricant Eye Drop

Soothe Tired Eyes Lubricant Eye Drop (Bausch & Lomb Inc.) is a preserved artificial tear whichis used to relieve the dryness of the eye and to prevent further irritation. Its active ingredient is glycerin 1%. The artificial tear will be applied topically to both eyes for 6 weeks with the following regimen: four times a day for 2 weeks, twice daily for 2 weeks, and once daily for 2 weeks.

In the case of increased intraocular pressure due to Lotemax, the medication will be tapered rapidly and stopped within 1 week. In addition, for cases where subjects withdraw from the study, the medication will be tapered and stopped within 1 week.

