3.2.2 Masking Procedures

The study drugs will be labeled by the Massachusetts Eye & Ear pharmacy with instructions for storage, the name of the study, an expiration date, and a notice that

the bottle may contain Lotemax. The pharmacy will maintain a master list of the participants' name, unique identifier, and the coded treatment assignment. The randomization scheme and treatment assignment will be held in the pharmacy to ensure that the investigator and study team remain masked. Participants, investigators, image analysts, and the sponsor (GSK) will be masked to the treatment group.

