3.2.3 Breaking the Mask

A subject's medication may be unmasked at any point for a medical emergency or to supplement a serious adverse event (SAE) report. The subjects will be unmasked at the end of the study in order to provide optimal ongoing care.

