8. SAFETY AND EFFECTIVENESS ASSESSMENTS

8.1 Safety Assessments

The primary safety variable monitored will be the occurrence of adverse events. The severity of each adverse event observed will be evaluated as serious or not serious and the occurrence will be evaluated as expected or unexpected. The relationship of the event to the study medication will be assessed by the investigator as possibly, probably, or definitely related. Safety variables will be evaluated at all study visits. If adverse events occur, the first concern will be the safety of the study participants. Any serious adverse event occurring during the study period will be immediately reported to MEEI IRB. At each visit throughout the study, the investigator will begin querying for adverse events by asking each subject a general, non-directed question such as "How have you been feeling since the last visit?" or "How have your eyes been since the last visit?"

The investigator will ask questions to subjects at each visit to determine if they have had any changes to the use of concomitant medications since the previous visit. A comprehensive eye examination including best-corrected visual acuity, measuring intraocular pressure, evaluation of the condition of conjunctiva, cornea, anterior chamber, iris/pupil, lens, vitreous, macula and optic nerve will be performed. Any changes in the study eyes from the screening visit will be recorded. If a subject contracts infectious conjunctivitis, they will be instructed to discard the remainder of the study drug and new drug will be sent from the host site pharmacy, Massachusetts Eye and Ear Infirmary.

If treatment with artificial tears is inadequate, or the subject develops severe form of ocular surface disease and dry eye, for the safety and proper treatment of the subject, the investigator can unmask the subject's treatment assignment to determine which

treatment has been assigned and institute appropriate follow-up care. However, the subject will be kept in the study so we can do the "intent-to-treat" analysis.

Withdrawal from the study will happen if any of the following occurs:

- Investigator determination that it is not in the best interest of the subject to continue participation.
- Subject's wish to withdraw for any reason.

After being withdrawn, subjects will be followed according to each case until the adverse event is resolved.

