11. DATA AND SAFETY MONITORING

11.1 Data and Safety Monitoring Plan

The PI, research fellows, research coordinators, and technicians involved with this protocol will be required to read the protocol, participate in a group meeting to discuss roles before the protocol is approved, and participate in weekly clinical research meetings. The pharmacy and the clinical fellows on the protocol will be required to read the protocol and separate meetings will be created to discuss roles as they relate to the protocol.

A copy of the approved protocol and study related materials will be placed on a shared network drive accessible to authorized research staff involved in this study and on IRBnet.org.

The primary safety variable monitored will be the occurrence of adverse events. The severity of each adverse event observed will be evaluated as outlined in section 10.6 by the treating investigator. The PI will be made aware of all AEs within one week. The number of AEs related to increased pressure will be monitored and collated throughout the course of the study. Should the investigator need to be un-masked to treatment assignment to determine if there is a relationship with one of the study medications, treatment information will be provided by the MEEI Pharmacy.

The ocular surface exam and IVCM imaging will only be performed by a research technician, fellow, or investigator to ensure adherence to the required tests and accurate assessments.

The study coordinator will be responsible for monitoring each visit to ensure that the procedures are performed as outlined in the protocol and documented appropriately.

The images acquired will be checked for accuracy by the research fellows after acquisition and also during image analysis to ensure that the nasal conjunctiva has been imaged appropriately as laid out in the IRB-approved protocol.

Raw data collected for this study will be entered into a master database by the study coordinator, research technician, or fellow and uploaded for access to the principal investigator and all authorized research staff members on the U-Drive of password-protected computers located in the Cornea Research Department.

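### The taper-and-stop rule for raised eye pressure in 5.1 names one arm's drug, so read literally a masked investigator can apply it only by obtaining the assignment

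*Combined protocol and SAP*

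**What the plan says.** Section 5.1 gives the plan's only pressure-specific action rule for an individual subject: "In the case of increased intraocular pressure due to Lotemax, the medication will be tapered rapidly and stopped within 1 week". It gives no pressure value. The only numeric pressure criterion is in 13.2, and it concerns stopping the whole study.

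The masking plan in 3.2.2 reads: "Participants, investigators, image analysts, and the sponsor (GSK) will be masked to the treatment group". The assignment list stays in the pharmacy.

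Grounds for breaking the mask appear in several places:

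- Section 3.2.3: "A subject's medication may be unmasked at any point for a medical emergency or to supplement a serious adverse event (SAE) report".
- Sections 5.5 and 8.1 add inadequate response to artificial tears and severe ocular surface disease. The subject then stays in the study for the intention-to-treat analysis.
- Section 11.1 first states "The number of AEs related to increased pressure will be monitored and collated throughout the course of the study". It then says of causality: "Should the investigator need to be un-masked to treatment assignment to determine if there is a relationship with one of the study medications", and has the pharmacy supply the information.

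Other parts of the plan need no knowledge of the arm. Section 8.1 (and 10.6 likewise) says: "The relationship of the event to the study medication will be assessed by the investigator as possibly, probably, or definitely related". Section 5.1 has a second trigger for tapering: "for cases where subjects withdraw from the study, the medication will be tapered and stopped within 1 week". Sections 8.1 and 9.3 list as a reason for withdrawal: "Investigator determination that it is not in the best interest of the subject to continue participation".

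**The concern.** In a double-masked trial, a rule for acting on a safety finding should rest on something that masked staff can observe. The trigger in 5.1 rests instead on which drug the subject received.

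Two things are at stake. The first is even handling: applied literally, the same pressure reading leads to a taper in one arm and not in the other. The primary analysis in 10.5 is by randomized assignment, so this would not invalidate the comparison by itself. It would make a stopping policy that operates in one arm only part of what is compared. The second is the mask. Each literal use of the rule in a subject who has not yet had the week 6 visit gives an investigator that subject's assignment before the final assessments, several of which are graded by an examiner or reported by the subject.

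**Working it through.** The point has no arithmetic beyond dates, so the check sets the sections side by side.

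**1. Can a masked investigator establish the trigger?** The condition has two parts: pressure is raised, and Lotemax caused it. The first is measured at each visit (7.8). The second is false for every artificial-tear subject, so establishing it requires the assignment that 3.2.2 withholds.

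**2. Does the plan provide a way to learn the assignment?** Yes. Section 11.1 allows it for judging relationship to a study medication, directly after the sentence on collating pressure-related adverse events. Section 9.1 also counts an abnormal finding as an adverse event if it leads to a change in study drug dosing, so a rise that triggers the taper falls within 11.1. Section 3.2.3, where staff would look first, does not list this ground, and 5.1 refers to neither section.

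**3. What routes are open when pressure is raised?**

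| Route | Needs the assignment | Acts on both arms | Mask kept for that subject | Later study procedures |
|---|---|---|---|---|
| 5.1 read literally, with unmasking under 11.1 | Yes | No, Lotemax only | No | Continue |
| Withdrawal by the investigator (8.1, 9.3), then the withdrawal taper in 5.1 | No | Yes | Yes | End (7.7); subject may be replaced (5.2) |
| 5.1 read as if it said study medication, judged as in 8.1 | No | Yes | Yes | Continue |

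The third route keeps both the mask and the follow-up, but it is not what 5.1 says. Staff could reasonably choose any of the three.

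**4. When does it matter?** Visit 2 is at week 2 ± 3 days: 14 − 3 = day 11 to 14 + 3 = day 17. Dosing runs to day 42 (Appendix V), so 42 − 17 = 25 to 42 − 11 = 31 days of scheduled dosing remain, and all week 6 assessments lie ahead. Visit 3 is at week 6 ± 1 week: 42 − 7 = day 35 to 42 + 7 = day 49. At most 42 − 35 = 7 days of dosing then remain, and no scheduled outcome follows. Among scheduled visits the problem is therefore essentially one of week 2. A rise found at an unscheduled visit before week 6 would raise it too.

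**5. Who could be affected by an unmasking?** Section 11.1 lets a technician, fellow or investigator perform the ocular surface exam and the confocal imaging. An investigator who has learned the assignment could therefore grade staining or tear break-up time, or acquire the primary-endpoint images, at week 6. The image analysts are masked under 3.2.2, and no section says that they would be told.

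**The case against.** The strongest reply is that the plan as a whole already answers the point. Section 3.2.3 is not worded as an exclusive list. Sections 5.5, 8.1 and 11.1 add grounds, and 11.1 covers causality. Withdrawal by the investigator needs no knowledge of the arm and leads to a taper within the same one week. The mention of Lotemax in 5.1 may also be shorthand for the presumptive, masked judgement that 8.1 and 10.6 use throughout, since 5.1 discusses pressure only for the steroid. Known steroid responders are excluded (4.2), so events may be few.

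Much of this stands, and it rules out two stronger readings that a reader might infer:

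- *That the rule cannot be carried out, or that opening the code is forbidden.* Section 11.1 permits unmasking, withdrawal is available, and silence in 3.2.3 is not a prohibition.
- *That people who assess later outcomes will learn the assignment.* The plan allows this for an investigator who also examines or images the subject, but does not establish that it would happen. Any unmasking is for one subject at a time.

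The reply does not remove the mismatch. The 11.1 route works by giving up the mask. The withdrawal taper in 5.1 is a separate, additional trigger, and using it for raised pressure costs the remaining assessments. The shorthand reading requires staff to depart from the text of a safety rule.

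**Conclusion.** The point holds as a conflict between a stated safety rule and the masking plan. Read literally, the pressure rule in 5.1 requires the assignment, uses an unmasking ground absent from 3.2.3, and treats the same finding differently by arm. It does not necessarily fail, and bias in the endpoints is possible but not shown.

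Its size cannot be calculated. The plan enrolls 50 subjects, about 50 / 2 = 25 per arm under 1:1 allocation, and gives no rate of pressure rises. Among scheduled visits the exposure is concentrated at week 2.

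The conclusion assumes that staff follow the wording of 5.1. If in practice every rise is judged against the study medication without unmasking, the arm-specific handling and the unmasking disappear, and only the wording needs correcting. In a small trial, even a few subjects unmasked before week 6 would be worth avoiding when the remedy is a change of text. A pressure rise may itself suggest the steroid arm; better wording would avoid confirming the assignment but would not remove that hint.

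**What to change.** Reconcile 5.1 with 3.2.2, 3.2.3, 8.1 and 11.1:

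- State the trigger in 5.1 in arm-neutral terms, referring to the study medication as 8.1 and 10.6 already do, so that a masked investigator can apply it to any subject. This alone resolves the conflict.
- If unmasking is to remain part of the rule, align 3.2.3 with 11.1, cross-refer from 5.1, and say who learns the assignment. Have that subject's later examinations, imaging and image analysis done by staff who remain masked. Adding the ground to 3.2.3 alone would largely repeat 11.1 and leave the arm-specific handling in place.
- Say whether a subject tapered for raised pressure stays in follow-up or counts as withdrawn under 7.7.

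The pressure threshold and the clinical action are for the sponsor's clinicians, and none is proposed here. The cost is protocol wording. Keeping the unmasking route would also require a second, masked assessor for the subjects concerned.

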5.2 Study Drug/Device Compliance/Adherence

Directed questioning using the (Ocular Tolerability and Compliance Questionnaire – Appendix I) will be administered by the investigator or research staff. Results on the participants' compliance and adherence to the study protocol and study drug will be recorded on the paper case report form (CRF) at the second and third visits (2 and 6 weeks after enrollment).

Subjects will not be withdrawn for lack of compliance with the study drug regimen.

During the study, all concomitant medication treatment regimens, ocular hygiene treatments (i.e., lid scrubs and warm compresses), or insertion of punctal plugs will be kept constant as permitted by accepted medical practice. If one of the aforementioned treatment regimens needs to be modified, the participant may be withdrawn based on the investigator's discretion.

Additionally, if there is an administration of a prohibited medication (including any other steroid) or procedure (any ocular surgery), the participant may be withdrawn based on the investigator's discretion.

Participants must be compliant with IVCM imaging on at least 2 of their 3 visits or they will be withdrawn. Subjects who are withdrawn may be replaced by new enrolled subjects to maintain the sample size in each group.

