7.7 Early Termination

If a subject withdraws or is withdrawn from the study prior to completion of all study visits, there will be no additional procedures performed

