10.5 Effectiveness Analysis

For efficacy variables and any other variables except for safety, all subjects will be analyzed with the treatment to which they were randomized (the intent-to-treat population). Subjects that are not compliant with the study medication or study procedures may or may not be withdrawn according to the investigators discretion. Subjects that are noncompliant, but remain active in the study, will be followed so that an intent-to-treat analysis can be conducted. For safety variables, subjects will be analyzed with the treatment actually received (the safety population).

The primary analysis for the proposed study will be based on a standard intention-to-treat analysis with each study participant analyzed with respect to the randomized treatment assignment, regardless of eventual compliance. A secondary analysis may include imputation of missing data for select variables. A per-protocol analysis, disqualifying subjects or subject visits, might also be done, but is not planned because observational analyses of actual treatment use could introduce bias if the pattern of use is in some way related to the outcome.

Despite the randomized nature of the treatment assignments, in this relatively small sample of study subjects there may be imbalances with regard to potential confounding variables. Thus, as an initial step in the analysis, we will compare those assigned to Lotemax versus those randomized to the artificial tear with regard to demographic characteristics and potential confounding variables, using the non-parametric Wilcoxon rank sum test for continuous or ordinal variables, and chisquare or Fisher's exact tests for categorical variables.

The changes in primary end-points within each group during the course of treatment will be analyzed using Analysis of Variance (ANOVA) with post hoc analysis of Bonferroni correction. The values between the Lotemax and artificial tear groups will be compared with non-parametric Wilcoxon rank sum test. P values of 0.05 or less will be considered as statistically significant.

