13. STUDY DISCONTINUATION CRITERIA

13.1 Discontinuation of Individual Research Subjects

Please see sections 9.3.

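### Sections 5.2 and 10.5 give opposite rules on withdrawing subjects who do not comply with study drug, and following 10.5 would selectively lose later outcome data, mainly at week 6

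*Combined protocol and SAP*

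**What the plan says.** On study-drug compliance, section 5.2 is categorical: "Subjects will not be withdrawn for lack of compliance with the study drug regimen". Section 10.5 says: "Subjects that are not compliant with the study medication or study procedures may or may not be withdrawn according to the investigators discretion". It then adds: "Subjects that are noncompliant, but remain active in the study, will be followed so that an intent-to-treat analysis can be conducted".

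Three other provisions decide what withdrawal means for the data:

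- Section 7.7, on subjects who leave before completing all visits: "there will be no additional procedures performed".
- Section 5.2, on replacement: "Subjects who are withdrawn may be replaced by new enrolled subjects to maintain the sample size in each group".
- Section 10.5, on the primary analysis: "each study participant analyzed with respect to the randomized treatment assignment, regardless of eventual compliance". Imputation appears there only as something a secondary analysis may contain.

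Section 10.5 also explains why no per-protocol analysis is planned: the amount of treatment a subject uses may be tied to outcome, so analysing by actual use could bias the result.

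On study procedures, 5.2 requires withdrawal of a subject who does not have IVCM at two or more of the three visits. Section 10.5 makes withdrawal for procedure non-compliance a matter of discretion.

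Section 13.1, on discontinuing individual subjects, says only "Please see sections 9.3". Section 9.3 lists the subject's best interest and the subject's own wish, and does not mention compliance.

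**The concern.** The two sections give opposite instructions for the same subject and the same reason. Someone who misses most of the drops stays in under 5.2 and has every planned assessment. Under 10.5 that person may be withdrawn, has no further assessments under 7.7, and may be replaced.

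What is at stake is outcome data after withdrawal. Compliance on treatment is recorded at weeks 2 and 6, so a subject withdrawn on the week-2 answers has no week-6 IVCM, and IVCM supplies all the primary endpoints in 10.1. The missing values would belong to subjects chosen for their compliance. Compliance may be related to response, for example through drop discomfort or lack of relief. That is the selection 10.5 seeks to avoid by not planning a per-protocol analysis, and here it would enter before the analysis begins.

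**Working it through.** **Step 1. Same subject, two rules.**

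| Question | Section 5.2 | Section 10.5 |
|---|---|---|
| Withdraw for study-drug non-compliance? | No | At the investigator's discretion |
| Withdraw for missed IVCM? | Yes, if missed at more than one of three visits | At the investigator's discretion |

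Section 10.5 names study medication expressly, so it cannot be read as covering procedures alone. Neither section defers to the other, and the route from 13.1 to 9.3 does not settle it.

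**Step 2. What withdrawal removes.** IVCM is scheduled at screening, week 2 and week 6. Withdrawal at the week-2 visit leaves baseline and usually week-2 data, and loses week 6. Withdrawal before week 2 loses both follow-up assessments.

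**Step 3. The IVCM rule.** Eligibility needs a baseline IVCM, so an enrolled subject falls below two of three visits only by missing both follow-up images. By then little scheduled IVCM data is left to lose. The conflict on procedures therefore matters mainly for replacement and for whether the subject is still counted in the analysis set.

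**Step 4. Possible size of the shift.** The plan states no figure on this point, so what follows is illustration.

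- From section 10.3: SD 44 and difference 52 cells/mm². Fifty subjects at 1:1 give 25 per arm.
- Assumed: share withdrawn f = 12% (3 of 25) or 20% (5 of 25), in one arm only, with withdrawn subjects differing from those kept by one SD.
- Full-arm mean = (1 − f) × kept + f × withdrawn, so kept − full = f × (kept − withdrawn).

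| Gap, kept vs withdrawn | f = 12% | f = 20% |
|---|---|---|
| 44 (one SD) | 0.12 × 44 = 5.3; 5.3/52 = 10% | 0.20 × 44 = 8.8; 8.8/52 = 17% |
| 22 (half an SD) | 0.12 × 22 = 2.6; 2.6/52 = 5% | 0.20 × 22 = 4.4; 4.4/52 = 8% |

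If both arms lose the same share with the same gap in the same direction, the shifts cancel in the between-arm difference.

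**Step 5. Effect estimated versus precision.** Assume 25 per arm, an equal share f non-compliant in each arm, no effect in non-compliant Lotemax subjects, SD 44 throughout and no replacement. Power = Φ(difference / (44 × √(2/n)) − 1.96).

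| f | Keep all: difference 52 × (1 − f), n = 25 | Withdraw: difference 52, reduced n |
|---|---|---|
| 10% | 46.8, power 96% | n = 22, power 97% |
| 20% | 41.6, power 92% | n = 20, power 96% |
| 30% | 36.4, power 83% | n = 18, power 94% |

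Under these assumptions, retention estimates the effect of assignment, which is what 10.5 says it wants. Withdrawal estimates something close to the effect in compliers. The choice of section changes the quantity estimated more than the precision.

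**The case against.** The strongest defence is that 10.5 loosely summarises 5.2: drug non-compliers stay, and those who miss too much imaging leave. The reference to investigator discretion does not fit that reading, because 5.2 leaves no discretion in either case. The conflict stands.

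Several stronger conclusions are tempting, and the documents do not support them:

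- *The primary analysis becomes a comparison of subjects the investigator chose to keep.* Section 10.5 still analyses everyone by assigned arm and does not remove withdrawn subjects from the intent-to-treat set. The defect is selectively missing later data without a primary method for it.
- *A withdrawn non-complier has no outcome data.* Earlier data remain, and neither 10.1 nor 10.5 names a single primary time point.
- *Section 10.5 contradicts itself.* Analysing by assignment "regardless of eventual compliance" concerns the analysis; following those who remain active concerns data collection. The two are in tension but are not opposites.
- *A few withdrawals use up the enrolment margin.* Replacement under 5.2 can restore numbers, though it does not restore the randomised comparison.
- *Different investigators would produce different data sets.* This is one site with weekly research meetings, so that is speculation.
- *Investigators could select by arm.* They are masked by default. Unmasking is possible in the situations the plan lists, and tolerability could still make compliance differ by arm, but the documents show no knowing selection.

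It is also fair to say that 9.3 concerns adverse events, so its silence on compliance is unremarkable. The withdrawal rates and the gap in the illustration come from no section of the plan.

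**Conclusion.** The concern holds in a limited form. Sections 5.2 and 10.5 conflict on withdrawal for study-drug non-compliance, and separately on withdrawal for missed IVCM. Combined with 7.7 and the replacement rule, following 10.5 on drug compliance would lose post-withdrawal outcomes, mainly week-6 IVCM, for subjects selected on compliance. That works against both the intent-to-treat principle in 10.5 and its stated reason for not planning a per-protocol analysis.

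The contradiction rests on the text alone. The size of any bias does not: 5.3 to 8.8 cells/mm² in one arm's mean requires a one-SD gap and 12% to 20% withdrawn in that arm only. With smaller gaps or similar withdrawal in both arms it is less, and if nobody is withdrawn for non-compliance it is nil.

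**What to change.** Reconcile 5.2, 7.7 and 10.5:

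1. In 10.5, remove discretionary withdrawal for non-compliance with study medication. State, in line with 5.2, that such non-compliance is not in itself a reason to end follow-up, and that the subject has the planned Visit 2 and Visit 3 assessments.
2. Treat non-compliance with procedures in its own sentence. Give one IVCM rule, worded identically in 5.2 and 10.5, either mandatory or discretionary.
3. In 7.7, make clear that assessments cease only for a subject who has left the study, and not for one who has missed or stopped study drug.
4. State that a replacement does not remove the original randomised subject from the intent-to-treat set.
5. Have 13.1 point to the reconciled rule as well as to 9.3.

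Keep ending follow-up distinct from stopping study drug. Section 5.1 ties withdrawal to tapering and stopping the medication, so the wording should not blur the two. This change prescribes no treatment-stopping rule.

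The cost is a few sentences. No visits are added beyond those already scheduled.
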